9.1 General Considerations

All statistical tests will be conducted at a two-sided 0.05 significance level.

Statistical tests for the primary and key secondary endpoints will be conducted using a fixed-sequence procedure according to the pre-specified order to maintain the overall Type I error rate to a two-sided 5%. All other secondary endpoints will be tested without adjustment for multiplicity.

Stool frequency and rectal bleeding scores at each visit will be calculated as an average of the daily scores collected within 5 days prior to the visit (excluding the visit day and the day before the visit day if the bowel preparation is needed on the day before the visit). If the daily scores in this period are available for fewer than 3 days, the average score will be considered missing. The average scores will be rounded to the nearest integer for the final score determination (e.g., 0.3 will be rounded to 0, and 0.5 will be rounded to 1).

The average scores will be calculated at Visit 2 (Week 2), Visit 3 (Week 4), and Visit 4 (Week 8) for the double-blind period, and Visit 6 (Week 10) and Visit 7 (Week 16) for the open-label period. Although both Visit 4 and Visit 5 are designated as Week 8 in the double-blind period, Visit 4 corresponds to the visit for the endoscopic assessment, and therefore, the stool frequency and rectal bleeding scores will be calculated at Visit 4. Similarly, the scores will be calculated at Visit 7 for the end of the open-label period instead of at Visit 8.

However, in one section (Section 7.1.3) of Protocol Amendment 2, it was unintentionally indicated that the scores would be calculated at Visit 5 and Visit 8 instead of Visit 4 and Visit 7. As a result, some of these subjects completed the diary fewer than 3 days within 5 days prior to Visit 4 and/or Visit 7 but completed 3 or more days prior to Visit 5 and/or Visit 8. Therefore, for those subjects who consented with Protocol Amendment 2, the average scores calculated at Visit 5 and/or Visit 8, as indicated in Section 7.1.3 of Protocol Amendment 2, will be used if the average scores at Visit 4 and/or Visit 7 are missing. Handling of other missing data in the statistical analyses will be described for each endpoint.

For the endoscopic assessment, the outcomes determined by the independent central reading procedure will be used for all analyses.

For visit-based data, the data collected on the day that is closest to the scheduled trial day within a window will be assigned to the corresponding analysis visit. [Table 2](#) and [Table 3](#) show the scheduled trial day and window for each analysis visit during the double-blind period and open-label period, respectively.

Table 2 Scheduled trial day and window for analysis visits: double-blind period

Analysis visit	Scheduled trial day	Window
Baseline	Day 1	prior to the first dose of IMP

Week 2	Day 15	Day 1 to Day 22
Week 4	Day 29	Day 23 to Day 43
Week 8	Day 57	Day 44 or after, but before 1st dose of OL period

OL: open label

Table 3 Scheduled trial day and window for analysis visits: open-label period

Analysis visit	Scheduled trial day	Window
Week 10	Day 71	After 1st dose of OL period up to Day 92
Week 16	Day 113	Day 93 or after

OL: open label

If the closest day cannot be uniquely identified for an analysis visit, the data collected on an earlier trial day will be assigned to the analysis visit.

The efficacy data captured during the 8-week open-label period will be descriptively summarized and used for exploratory purposes only.

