### **7.1.3 Subject Daily Diary**

The subject daily diary will be completed by the subject every evening starting the day of randomization (Visit 1/Day 1). Subject diary will consist of questions regarding IMP daily intake, stool frequency, and presence of blood content. The score for stool frequency and rectal bleeding will be calculated as an average based on scores collected from 3 day subject recall at Visit 0 or from subject diary data 5 days prior to Visits 2, 3, 4, 6 and 7 (see [Appendix 2](#)). If a subject recorded fewer than 3 days of scores during this 5-day period, the average score will be considered missing.

The subject daily diary and questionnaire will be completed via a validated Interactive Voice Response system (IVRS). Instructions on the use of the subject daily diary and questionnaire will be provided to each trial center.

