3.2 Determination of Sample Size

The true remission rates at Week 8 for mesalamine 4 g extended-release granules (sachet) and placebo regimens were assumed as 36% and 18%, respectively, based on Kamm et al. (2007)(3), Lichtenstein et al. (2007)(4), and Marteau et al. (2005)(5). Under these assumptions, a sample size of 110 randomized subjects per group will provide at least 85% power to detect a statistically significant treatment group difference in the remission rate at a two-sided 0.05 significance level using the chi-square test.

4 Subject Disposition

The number of screened subjects will be summarized, and for subjects not randomized, the primary reason for exclusion from randomization will be summarized.

The number and percentage of subjects who are randomized, are treated with IMP, prematurely discontinued, and completed the double-blind period of the trial will be summarized with the reason of premature discontinuations. Similar summaries will be made for subjects who are enrolled to the 8-week open-label period.

The time to discontinuation will be summarized by the Kaplan-Meier estimates, and the treatment group difference will be tested by the log-rank test. In addition, reason-specific discontinuation will be summarized by the cumulative incidence estimates.

5 Protocol Deviations

The following protocol deviations will be identified as major protocol deviations:

- Overall IMP compliance of less than 80% during the double-blind period
- Not taking the randomized IMP
- Taking prohibited medications during the double-blind period

The final definition of major protocol deviations will be determined prior to breaking the blind.

The number and percentage of subjects with protocol deviations will be summarized.

6 Analysis sets

For each analysis set, the number and percentage of subjects excluded from it will be summarized by the reason of the exclusion.

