9.2 Primary Endpoint(s)

9.2.1 Primary Variable(s) Analysis

The primary efficacy analysis will be based on all randomized subjects (ITT analysis set). The proportion of subjects with remission, defined as rectal bleeding score of 0 and stool frequency score of “0” or “1 with at least 1 point decrease from baseline” with an endoscopic score of 0 or 1 in the Clinical and Endoscopic Response Score at Week 8, will be compared between treatment groups using a chi-square test without a continuity correction at a two-sided 0.05 significance level. Subjects who discontinue the double blind regimen before Week 8, as well as subjects with missing remission assessment at Week 8, will be considered not having achieved remission. The odds ratio for the treatment group compared to the control group will be estimated and its 95% confidence interval will be provided using the Woolf’s approximation (Woolf, 1955)(6).

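### When the bowel-preparation day is dropped before Visit 4, SAP 9.1 does not replace it or move the look-back, so affected subjects need 3 of 4 diary days rather than 3 of 5.

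*SAP*

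**What the plan says.** SAP 9.1 takes the stool frequency and rectal bleeding scores at each visit as the mean of the daily diary scores in the 5 days before it, "excluding the visit day and the day before the visit day if the bowel preparation is needed on the day before the visit". The minimum follows: "If the daily scores in this period are available for fewer than 3 days, the average score will be considered missing". Nothing adds a day, moves the window or changes the minimum when the preparation day is removed.

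The Week 8 scores are taken at Visit 4, the endoscopy visit. Visits 2 and 3 have no endoscopy, so the preparation exclusion has no role there. In the double-blind period it can affect only the visit that supplies the Week 8 remission scores.

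Under SAP 9.2.1, subjects who discontinue early, "as well as subjects with missing remission assessment at Week 8, will be considered not having achieved remission". SAP 9.3.1 applies the same rule to the first key secondary endpoint. Subjects who consented under Protocol Amendment 2 may use Visit 5 scores when those at Visit 4 are missing. SAP 9.1 gives other subjects no such fallback.

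Protocol 7.1.3 has the 5-day period and the 3-day minimum ("If a subject recorded fewer than 3 days of scores during this 5-day period") but no preparation-day exclusion. SAP section 12 nevertheless declares no departure from the protocol analysis.

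**The concern.** Removing the preparation day is not in dispute. The problem is that the look-back was not moved by one day to make up for it. With five usable days a subject can miss two evenings and still have a score. With four, the second missed evening makes the score missing, and the subject is a primary-endpoint failure even if the endoscopy was done and the disease is in remission.

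If diary loss is equal in the two arms, both remission rates shrink by the same factor. Their ratio stays at 2, but the difference, and with it the power, falls. The same happens to the first key secondary endpoint, which must succeed before the second can be declared significant.

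**Working it through.** **Inputs from the documents.** SAP 3.2: "placebo regimens were assumed as 36% and 18%, respectively"; "a sample size of 110 randomized subjects per group will provide at least 85% power"; the test is "at a two-sided 0.05 significance level using the chi-square test", without continuity correction (SAP 9.2.1). No inflation for dropout is stated.

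**Assumptions, because the documents give no figures.** Evening completion c is 95, 90, 85 or 80%. Evenings are missed independently and equally in both arms. Every subject needs day-before preparation. Nobody uses the Visit 5 fallback. The 36% and 18% are rates before diary loss.

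**Step 1: the plan's power.** The pooled rate is 0.27. The normal approximation gives

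z = [0.18 − 1.96 × √(2 × 0.27 × 0.73/110)] / √[(0.36 × 0.64 + 0.18 × 0.82)/110] = (0.18 − 0.1173)/0.0586 = 1.07, a power of 85.7%.

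Full enumeration of the uncorrected chi-square test gives 86.0%. The stated figure of at least 85% reproduces, with about one point to spare.

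**Step 2: chance that the score is missing** (fewer than 3 recorded days).

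- Four usable days: 1 − c⁴ − 4c³(1−c)
- Five usable days: 1 − c⁵ − 5c⁴(1−c) − 10c³(1−c)²

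At c = 0.85:

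- Four days: 1 − 0.5220 − 0.3685 = 0.1095
- Five days: 1 − 0.4437 − 0.3915 − 0.1382 = 0.0266

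**Step 3: power.** Multiply both remission rates by (1 − missing) and enumerate again. At c = 0.85, four days give 32.06% v 16.03%, and five days give 35.04% v 17.52%.

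| Evenings completed | Missing, 3 of 4 | Missing, 3 of 5 | Power, 3 of 4 | Power, 3 of 5 |
|---|---|---|---|---|
| 95% | 1.4% | 0.1% | 85.3% | 85.9% |
| 90% | 5.2% | 0.9% | 83.4% | 85.5% |
| 85% | 11.0% | 2.7% | 80.1% | 84.7% |
| 80% | 18.1% | 5.8% | 75.7% | 83.1% |

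**Step 4: remitters lost.** The plan expects 0.36 × 110 = 39.6 plus 0.18 × 110 = 19.8, or 59.4 remitters. The extra loss under 3 of 4 is 59.4 times the gap between the two missing rates: about 0.8, 2.6, 4.9 and 7.3 remitters at 95, 90, 85 and 80% completion.

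**Step 5: weaker assumptions.** If half the subjects need preparation, the missing rate at 90% completion is (5.23 + 0.86)/2 = 3.04%, and power is 84.5%. If missed evenings cluster (lag-1 correlation 0.3 to 0.5, 85% completion), the score is missing in 15–17% under 3 of 4 and 7–10% under 3 of 5. The gap remains.

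**The case against.** The strongest reply is that SAP 9.1 never says four days. The visit day is not a day before the visit, so naming it as excluded makes sense mainly as a counting rule: take five days, skipping these. On that reading five days remain and nothing extra is lost. The reading is possible. The fixed window is more natural, because the period is defined from the visit and days are then taken out of it, and later in the same section the shortfall is again counted within 5 days of Visit 4. If both readings stand, two programmers could derive different primary results from one diary, which the same sentence in the SAP would cure.

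The following also stands:

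- The exclusion is conditional. Sigmoidoscopy is the default examination, and the share needing day-before preparation is not given.
- Diary completion may be high. Subjects unable to complete the diary are excluded, and compliance is reviewed at visits.
- If the planning rates already counted missing as failure, part of the loss is counted twice.
- A constant minimum of 3 days is defensible in itself, and loss that is equal in both arms does not favour mesalamine.
- SAP 9.2.2 imputes missing Week 8 scores by multiple imputation and pattern-mixture models. These would show whether diary loss matters, but they leave the primary result unchanged.

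Three stronger inferences are tempting and not supported:

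- A reader might take the SAP's remark that "some of these subjects completed the diary fewer than 3 days within 5 days prior to Visit 4" as evidence of how often this rule bites. The SAP attributes that shortfall to Amendment 2 naming the wrong visits, and rescues those subjects with Visit 5 scores.
- A reader might see a separate bias in the longitudinal analysis of clinical remission, since only Week 8 has the stricter rule. That analysis estimates the treatment odds ratio within each time point, so lower Week 8 rates in both arms bring only the same loss into the treatment comparison.
- A reader might blame this rule for the whole fall below 85% power. At 85% and 80% completion, 3 of 5 also falls short (84.7% and 83.1%). That part is due to incomplete diaries.

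**Conclusion.** The point holds as a conditional one. On the natural reading, subjects who need day-before preparation at Visit 4 are held to 3 of 4 diary days, and failing that makes them non-remitters in the primary and first key secondary endpoints, unless they consented under Amendment 2 and have usable Visit 5 scores.

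The cost of the rule is the difference between the two power columns: 0.6 points at 95% completion, about 2 at 90%, 4.5 to 4.6 at 85% and 7.4 at 80%. These figures assume universal day-before preparation, independent evenings, equal loss in both arms, no fallback, and planning rates before diary loss. The documents do not show where the trial lies in this range, so they do not establish that it is underpowered. The change is worth making because it is cheap and removes an ambiguity from the primary endpoint.

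**What to change.** In SAP 9.1, state that when the day before Visit 4 or Visit 7 is excluded for bowel preparation, the score averages the 5 calendar days before the preparation day (Day -6 to Day -2 relative to the visit), with the minimum of 3 recorded days kept. Decide this before unblinding. List the preparation-day exclusion and the moved window in SAP section 12 as differences from Protocol 7.1.3. If the protocol text is to be aligned as well, that takes an amendment under Protocol 12.1.

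The cost is one sentence and a changed derivation. The diary runs daily from Day 1, so no new data are needed, and the rule does not depend on treatment. The downside is that one diary day is a day older. For the earliest Visit 4 (Day 57 − 6 = Day 51), the oldest day becomes Day 51 − 6 = Day 45, still inside the SAP's Week 8 window, which opens on Day 44.

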## 9 STATISTICAL METHODS

All analyses will be detailed in a subsequent statistical analysis plan.

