9.2.2 Sensitivity Analyses

The following sensitivity analyses will be conducted to assess the robustness of the primary analysis:

- As-treated analysis based on actually received treatment
- Analysis on the mITT analysis set
- Analysis on the PP analysis set
- Analysis using the last observed Clinical and Endoscopic Response Score
- Fisher-exact test combined with Cornfield’s exact 95% CI (Cornfield, 1956)(7)

The same analysis conducted for the primary analysis will be repeated for these sensitivity analyses.

Since the definition of remission was modified during the study, an analysis based on the original definition, i.e., rectal bleeding and stool frequency scores of 0 with an endoscopic score of 0 or 1 in the Clinical and Endoscopic Response Score, will also be conducted for reporting purpose.

In addition, sensitivity analyses using multiple imputation (MI) methods and pattern mixture models (PMMs) under missing at random (MAR) and missing not at random (MNAR) assumptions, respectively, will be conducted.

Under the MAR assumption, the missing stool frequency and rectal bleeding scores (Clinical Response scores) for Weeks 2, 4, and 8 will be imputed sequentially by regression-based imputation models using treatment group, baseline characteristics, and outcomes from preceding visits as the predictors. Once the missing Week 8 Clinical Response scores have been imputed, Week 8 Endoscopic Response score will be imputed by regression-based imputation models using treatment group, baseline characteristics, and Week 8 Clinical Response scores as the predictors. Based on the imputed Clinical and Endoscopic Response scores, the remission status at Week 8 will be determined. This imputation procedure will be repeated 100 times, and the primary analysis method will be applied to each of the imputed dataset. A combined estimate of the odds ratio for the treatment group compared to the control group and its 95% confidence interval will be obtained by the methods described in Rubin (1987)(8).

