9.3.2 Other Secondary Endpoints

The following secondary endpoints will be analyzed for the ITT analysis set.

- The proportion of subjects with endoscopic improvement, defined as an Endoscopic Response Score of 0 or 1, with at least a 1 point reduction from baseline in the endoscopic score at week 8
- The proportion of subjects in clinical remission at Weeks 2, 4, and 8, defined as a score of 0 for rectal bleeding and “0” or “1 with at least 1 point reduction from baseline” for stool frequency in the Clinical Response Score subset
- Time to normal stool pattern, defined as time in days from randomization to the first day of 3 consecutive days with a stool frequency score of 0, based on subject daily diary
- The change from baseline in rectal bleeding score at Weeks 2, 4, and 8, based on subject daily diary
- The change from baseline in serum CRP levels at Weeks 2, 4, and 8
- The change from baseline in fecal calprotectin levels at Week 8

The proportion of subjects with endoscopic improvement will be analyzed using the same statistical method used for the primary efficacy analysis.

The proportion of subjects in clinical remission at Weeks 2, 4, and 8 will be analyzed by the generalized estimating equations (GEE) approach as longitudinal binary outcomes. The model will include treatment, time, and treatment- by-time interaction. The clinical remission rates and odds ratio will be estimated for each time point. The overall treatment difference over 8 weeks will be estimated as the main effect for treatment in the model. The missing values will be imputed as non-remission, and an unstructured working correlation matrix will be used.

The time to normal stool patten will be analyzed using the same statistical method used for the analysis of the time to cessation of rectal bleeding.

The change from baseline in rectal bleeding score and serum CRP levels at Weeks 2, 4, and 8 will be analyzed by repeated-measures analysis of covariance (ANCOVA) models that include treatment, time, and treatment-by-time interaction as fixed effects, and the corresponding baseline value as a covariate. The adjusted changes from baseline and their difference between treatment groups will be estimated for each time point. The overall treatment difference over 8 weeks will be estimated as the main effect for treatment in the model. The missing values will be left as missing, and an unstructured correlation matrix will be assumed.

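### SAP 9.3.2 does not say whether the change-from-baseline bleeding model uses the rounded or the unrounded diary average; using the rounded one would lose precision for no purpose (minor)

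*SAP*

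**What the plan says.** SAP 9.1 defines one visit-level score for each diary item: "Stool frequency and rectal bleeding scores at each visit will be calculated as an average of the daily scores collected within 5 days prior". That window ends at the visit, and at least three recorded days are needed. The days left out are given as "excluding the visit day and the day before the visit day if the bowel preparation is needed on the day before the visit". The section then adds: "The average scores will be rounded to the nearest integer for the final score determination (e.g., 0.3 will be rounded to 0". Its second example turns 0.5 into 1. It lists the post-baseline visits at which averages are formed and does not mention the baseline recall.

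SAP 9.3.2 takes up the bleeding score as a secondary endpoint: "The change from baseline in rectal bleeding score and serum CRP levels at Weeks 2, 4, and 8 will be analyzed by repeated-measures". The model is an ANCOVA with treatment, time, their interaction and the baseline value as terms and an unstructured correlation matrix. The section does not say whether the score is the average or the rounded average.

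Protocol 7.1.3 has the average but no rounding: "The score for stool frequency and rectal bleeding will be calculated as an average based on scores collected from 3 day subject recall". The recall belongs to Visit 0; later visits use five days of diary. Protocol section 9 leaves detail to the SAP: "All analyses will be detailed in a subsequent statistical analysis plan".

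The remission criterion in SAP 9.2.1 does need whole numbers. It is "defined as rectal bleeding score of 0 and stool frequency score of", followed by the two permitted stool values: zero, or one after a one-point fall.

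**The concern.** Remission is a yes/no criterion on whole-number scores, so an average has to be turned into an integer somehow. The change-from-baseline model has no such criterion. It compares mean changes, and an average over several days is a better measurement for that purpose than the same average forced onto 0, 1, 2 or 3.

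Because SAP 9.1 rounds without limiting the rule to particular endpoints and SAP 9.3.2 is silent, two programmers could build different outcome variables from the same plan. At stake is the precision of one secondary comparison and the reproducibility of its result. Its validity is not at stake, and neither is the primary test.

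**Working it through.** **The plan's own figure.** The SAP gives no power for the bleeding model. Its stated power, at least 85% for the primary test (SAP 3.2: 36% vs 18%, 110 per group, two-sided 0.05, chi-square), reproduces. With pooled p = 0.27, z = [0.18√110 − 1.96√(2·0.27·0.73)] / √(0.36·0.64 + 0.18·0.82) = (1.888 − 1.231)/0.615 = 1.07, which gives 85.7%. Exact enumeration of the uncorrected chi-square test gives 86.0%. The sample size is not in question.

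**What rounding removes.** With n recorded days scored 0 to 3, the average can take 3n + 1 values: 10, 13 or 16 for n = 3, 4 or 5. Rounding leaves 4. The score moves by up to 0.33 (3 days), 0.5 (4 days) or 0.4 (5 days) on a 0–3 scale. For example, five-day averages of 0.6 and 1.4 both become 1, while 0.4 and 0.6 become 0 and 1.

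**Effect on power at Week 8.** All inputs here are assumptions, because the documents give none.
- Design: 110 per arm, changes at Weeks 2, 4 and 8, the SAP 9.3.2 terms, unstructured covariance, 2000 runs per scenario.
- Daily score: subject latent mean plus daily noise, rounded and clipped to 0–3.
- Baseline: 3 days, latent mean 1.5.
- Placebo Week 8 latent mean: 0.6 or 0.9.
- Between-subject SD 0.4, 0.6 or 0.8, paired with a Week 8 latent effect of 0.20, 0.25 or 0.30 (40% of it at Week 2, 70% at Week 4).
- Daily SD: 0.4 or 0.6.
- Correlation: 0.4 with baseline, 0.55–0.7 between visits.

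That is 2 × 3 × 2 = 12 combinations in each of three settings, or 36 scenarios.

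| Setting | Power, unrounded | Power, rounded |
|---|---|---|
| No dropout, 5 diary days | 72–92% | 65–80% |
| 20% dropout, 5 days | 65–86% | 58–70% |
| 20% dropout, 4 days at Week 8 | 59–84% | 54–70% |

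The unrounded score had higher power in all 36 scenarios, by 5 to 16 points, or by 4 to 15 points if only the visit score and not the baseline is rounded. In four null settings, rejection was 4.8–6.6% unrounded and 5.1–5.9% rounded. A simpler Week 8 ANCOVA at the same sample size, in 24 assumed settings, also favoured the unrounded score every time, by about 5 to 16 points, with null rejection near 5% for both.

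**Remission, for the optional item.** Enumerating all diary patterns under half-up rounding, those with recorded blood that score 0 are:
- one streak day among 3, 4 or 5 recorded days (averages 0.33, 0.25, 0.20);
- with 5 recorded days only, two streak days or one day of obvious blood (average 0.40).

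With 4 recorded days, for instance if a bowel-preparation day is dropped and not replaced, the last two patterns average 0.5 and become 1.

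SAP 9.2.2 introduces its list with "The following sensitivity analyses will be conducted to assess the robustness of the primary analysis". The list varies population, missing-data method, test and the stool-frequency criterion. Nothing on it varies the rounding.

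**The case against.** **The rounding sentence may already exclude the model.** It ends with a purpose clause about determining the final score, which could cover only the categorical criteria. That is a fair reading, and a reader who infers that the SAP literally prescribes rounding in SAP 9.3.2 goes further than the text. What stands is that the SAP does not say which reading applies.

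**Little depends on this endpoint.** It lies outside the fixed sequence and is tested without multiplicity adjustment, and the rounded model is valid. This is accepted, and it is why the point is minor. The power gains are also not adjusted for test size. With 2000 runs the Monte Carlo standard error at 5% is √(0.05·0.95/2000) = 0.49 points, so the 6.6% null result is (6.6 − 5)/0.49 = 3.3 standard errors high. The simpler ANCOVA, with null rejection near 5% for both versions, shows the same gain, so the direction does not rest on that excess.

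**A stronger reading is tempting: that remission is mis-scored because a subject with recorded blood can score 0.** The documents do not support it. In SAP Table 1 the no-blood grade belongs to a daily subscale, the visit score is an average in both documents, and SAP 9.1 discloses the tolerance with its own example. The rule is prespecified and the same in both arms. Some integer rule is needed, because averages between 0 and 1 are otherwise undefined for stool frequency. Nor is it a protocol deviation, since Protocol 7.1.3 leaves the step open and Protocol section 9 defers detail to the SAP.

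**Another is that the primary result is fragile to the rule.** Starting from an illustrative 40 vs 20 remitters of 110, removing 30% on mesalamine and 10% on placebo gives 28 vs 18 (p = 0.097); the reverse gives 36 vs 14 (p = 0.0004). Nothing in the documents points to either split. The share of remitters with recorded blood is unknown, because remitters must also meet the stool and central endoscopy criteria.

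**Conclusion.** The concern holds as a minor point about SAP 9.3.2. The plan leaves open which bleeding score enters the change model, and the rounded version would cost precision for no purpose. The cost is about 5 to 16 percentage points of power at Week 8 under the assumed inputs, without a material effect on type I error. The direction was the same in every scenario tried; the size depends on assumptions about bleeding levels, variability and the treatment effect that the documents do not supply.

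The rounded score as the primary remission definition is not an error, and the effect of rounding on the primary result is unknown in size and direction. A reader might also infer that remission should be re-tested requiring zero bleeding on every recorded day. That goes too far: such a rule is easier to pass with fewer entries. At a 20% daily chance of blood and independent days, 0.8³ = 51% pass with 3 recorded days and 0.8⁵ = 33% with 5. A descriptive count is enough. Nor can it be said that the information would be lost, because Protocol 9.6.1 calls for all data to be listed by subject and visit, and the SAP's table and listing shells are in a separate document.

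**What to change.** **Main change.** Add to SAP 9.3.2: *The rectal bleeding score in this model is the unrounded average, at baseline and at each visit.* It uses diary and recall data already collected and leaves the primary analysis, the alpha and the sample size unchanged. The only downside is that the modelled score is no longer an integer from 0 to 3.

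**Optional.**
- Tabulate, by arm, the Week 8 remitters whose bleeding average is above 0 and below 0.5, with the number of recorded diary days behind each average. Label it as description, with no further hypothesis test. It costs one table.
- State in SAP 9.1 whether the baseline recall average is rounded when the one-point fall in stool frequency is judged. It costs one sentence.

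Keep the rounded score as the primary definition of remission.
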